5.4 PARTICIPANT WITHDRAWAL OR TERMINATION

5.4.1 REASONS FOR WITHDRAWAL OR TERMINATION

Participants are free to withdraw from participation in the study at any time upon request. An investigator may terminate participation in the study if:

- Any clinical adverse event (AE), laboratory abnormality, or other medical condition or situation occurs such that continued participation in the study would not be in the best interest of the participant
- The participant meets an exclusion criterion (either newly developed or not previously recognized) that precludes further study participation.

5.4.2 HANDLING OF PARTICIPANT WITHDRAWALS OR TERMINATION

Subjects may withdrawal from the study at any time. Subjects that choose to withdraw early from the study will be voluntarily surveyed for reasons for withdrawal. They will be asked for permission to continue to utilize the data collected up to the point of withdrawal for research purposes. Should they decline, all data past the note of withdrawal will be deleted from the record system. Subjects will not automatically have their stimulation device removed. Spinal cord stimulator devices will be removed electively, if the device malfunctions, or if the device poses a significant risk to the subject's health.

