5.3 STRATEGIES FOR RECRUITMENT AND RETENTION

Subjects will be recruited via flyer made available at each site through the neurosurgery and PM&R clinics. We anticipate limited enrollment during the first year to establish and test trial infrastructure. Expansion through the additional sites and capacity should double each year until target enrollment. After securing the initial funding source, our clinic receives weekly inquiries about the status of the proposed trial, highlighting the existing potential recruitment network. We anticipate flyers to be widely disseminated throughout this network.

Patients with chronic SCI are highly motivated and very involved in their care. Subjects will be in continuous contact with the study as they complete their home rehabilitation regimen and will be seen on a monthly basis for testing.

Subjects will receive appointment reminders the week prior to their appointments and regular phone calls if their home rehabilitation progress becomes delayed by more than one week.

Subject recruitment will be divided into two phases. In phase 1, 10 subjects will be recruited per protocol. After the recruitment of the 10th subject, recruitment will be temporarily halted. After the 6 month timepoint data collection for these 10 subjects, the safety endpoints and adverse event reports will be submitted to the FDA in a summary format. Recruitment will not continue until FDA review and approval, though additional subjects may be screened and potentially scheduled.

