7.3.6 EARLY TERMINATION VISIT

Should the subject be terminated from the study for any reason, their final visit will consist of basic safety screening: a complete physical exam, the Vital Signs and Tests assessment and the Modified Ashworth Scale Assessment if the participant is willing. If the subject's device remains intact, it will be interrogated to check impedances.

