8.3 TIME PERIOD AND FREQUENCY FOR EVENT ASSESSMENT AND FOLLOW-UP

The occurrence of an AE or SAE may come to the attention of study personnel during study visits and interviews of a study participant presenting for medical care, or upon review by a study monitor. All AEs including local and systemic reactions not meeting the criteria for SAEs will be captured on the appropriate CRF. Information to be collected includes event description, time of onset, clinician's assessment of severity, relationship to study product (assessed only by those with the training and authority to make a diagnosis), and time of resolution/stabilization of the event. All AEs occurring while on study must be documented appropriately regardless of relationship. All AEs will be followed to adequate resolution.

Any medical condition that is present at the time that the participant is screened will be considered as baseline and not reported as an AE. However, if the study participant's condition deteriorates at any time during the study, it will be recorded as an AE. UPs will be recorded in the data collection system throughout the study. Changes in the severity of an AE will be documented to allow an assessment of the duration of the event at each level of severity to be performed. AEs characterized as intermittent require documentation of onset and duration of each episode. The PI will record all reportable events with start dates occurring any time after informed consent is obtained until 7 (for non-serious AEs) or 30 days (for SAEs) after the last day of study participation. At each study visit, the investigator will inquire about the occurrence of AE/SAEs since the last visit. Events will be followed for outcome information until resolution or stabilization.

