8.4.2 SERIOUS ADVERSE EVENT REPORTING

AEs will be followed until resolution even if this extends beyond the study-reporting period. Resolution of an AE is defined as the return to pretreatment status or stabilization of the condition with the expectation that it will remain chronic.

Any AE that meets a protocol-defined serious criterion must be submitted immediately (within 24 hours of site awareness) on an SAE form to the IRB and FDA. The principal investigator will be notified of the SAE by the FDA. The principal investigators monitor will review and assess the SAE for regulatory reporting and potential impact on study subject safety and protocol conduct.

At any time after completion of the study, if the investigator becomes aware of an SAE that is suspected to be related to study product, the investigator will report the event to the IRB and FDA.

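### On refusal, the withdrawal rule in 5.4.2 deletes data after the withdrawal note with no safety exception, which contradicts the adverse event recording and follow-up rules in 8.3 and 8.4.2

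*Combined protocol and SAP*

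**What the plan says.** Section 5.4.2 sets out what happens when a subject chooses to leave early. On data use: "They will be asked for permission to continue to utilize the data collected up to the point of withdrawal for research purposes". On refusal: "Should they decline, all data past the note of withdrawal will be deleted from the record system". On the implant: "Subjects will not automatically have their stimulation device removed".

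Other sections require safety information from the period after withdrawal:

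- Section 7.3.6, early termination: "Should the subject be terminated from the study for any reason, their final visit will consist of basic safety screening". The visit comprises a physical examination, vital signs and the Modified Ashworth Scale, with an impedance check if the device is intact. The text adds a condition about the participant's willingness.
- Section 8.3 has events recorded from consent "until 7 (for non-serious AEs) or 30 days (for SAEs) after the last day of study participation".
- Section 8.4.2: "AEs will be followed until resolution even if this extends beyond the study-reporting period".

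Three further sections bear on what is kept or summarised. Section 10.4.2 includes dropouts' data in the final analysis unless the subject asked for removal. Section 10.4.4 describes the safety summaries and has no removal clause. Section 14.2 requires retention of completed case report forms, source documents and copies of adverse event reports. Section 5.3 adds a checkpoint after the first 10 subjects reach month 6, when "the safety endpoints and adverse event reports will be submitted to the FDA in a summary format". Recruitment waits for FDA review.

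**The concern.** The question put to the subject and the consequence of the answer concern different data. The subject is asked about data from before withdrawal, and a refusal deletes data from after it. No exception is made for safety records in 5.4.2 or elsewhere.

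Most of what the plan schedules after a withdrawal is safety information, so the rule acts mainly on records that other sections oblige the investigators to make. The implant normally stays in place, and 6.1.11 plans for 6.5 years of implantation, so device and surgical risk does not end with participation. The protocol's own figures from other stimulator studies (2.3.1) are not trivial: lead migration 14% retrospectively and 10–59% prospectively, lead breakage 17% and 4%, infection 3% and 3–4%. Safety oversight rests with the principal investigator (8.6), and the plan names no independent committee that would hold a parallel record. Deleted records cannot be recovered at analysis.

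**Working it through.** No calculation in the plan is at issue. The check sets the sections side by side under each possible meaning of *past the note of withdrawal*, for a subject who chooses to withdraw and refuses permission.

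| Record | Where required | Literal reading (after the note) | If *prior* was meant |
|---|---|---|---|
| Adverse events and case report forms made on study | 8.3, 14.2 | Kept | Deleted |
| Non-serious events starting up to 7 days after participation | 8.3 | Deleted | Kept |
| Serious events starting up to 30 days after participation | 8.3 | Deleted | Kept |
| Follow-up of open events to resolution | 8.3, 8.4.2 | Deleted | Kept |
| Termination-visit findings obtained after the note | 7.3.6, if willing | Deleted | Kept |
| Efficacy data gathered before withdrawal | Subject of the permission request | Kept, although use was refused | Deleted |

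**How much of the windows is affected.** The last day of participation is not defined for a subject who withdraws. Let the note be written *d* days after that day, with *d* at least 0. The parts of the 8.3 windows that fall after the note are max(0, 7 − *d*) days for non-serious events and max(0, 30 − *d*) days for serious events. With *d* = 0 these are the full 7 and 30 days. If the termination visit counts as the last day and follows the note, both windows again lie wholly after the note. Follow-up to resolution has no end date, so it falls after the note for any event still open then.

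**Literal reading.** Section 5.4.2 deletes what 8.3 and 8.4.2 require. It also fails in its apparent purpose, because the data the subject declined to share remain in the system. Section 10.4.2 would then include those data unless the refusal counts as a request for removal, which neither section says.

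***Prior* reading.** This fits the permission question better and is compatible with 10.4.2. But it deletes on-study adverse events that 8.3 says must be documented regardless of relationship, and case report forms and source documents that 14.2 says must be retained.

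Neither reading is consistent with the rest of the protocol, and no other section decides between them.

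**Size.** The effect on safety summaries would be the number of subjects who withdraw and refuse, times the events per such subject in the deleted period. The documents give neither factor. The 25% in 10.5 is non-attendance at sessions, not withdrawal, and cannot stand in for the first.

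**The case against.** The best answer is that the protocol has other routes for safety data. Section 8.4.2 sends any serious event to the IRB and FDA within 24 hours of site awareness, and 8.4.1 sends all adverse events to the IRB and sponsor within 30 days. Deletion from the study's record system does not recall those reports, and 14.2 requires copies of adverse event reports to be kept. This stands. It limits the main loss to the study's own record: non-serious events, termination-visit findings, outcomes of open events, and the summaries built on them. It does not remove the contradiction.

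The scope is also narrow. The rule reaches only subjects who choose to withdraw and then refuse, not those whom the investigator terminates under 5.4.1. The termination visit depends in part on willingness, and 7.3.6 does not place it before or after the note, so that conflict is weaker than the one with 8.3 and 8.4.2. Nor is everything after the note safety data: the voluntary survey of reasons for leaving, and home accelerometry uploaded late, could also fall there.

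A reader might infer that a serious event would vanish from the FDA's view at the 10-subject checkpoint. The 24-hour rule means that the FDA should already hold that report; what could be incomplete is the study's summary. A reader might also infer that an event already counted under the halting rule in 8.5 would be struck out. An event already counted would normally precede the note, so this needs the *prior* reading, and 8.5 acts when the third event is reported, with nothing to say that the count is redone after a deletion.

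**Conclusion.** The rule is wrong as written. For subjects who withdraw and refuse, the literal text orders deletion of records that 8.3 and 8.4.2 require, plus any termination-visit findings obtained after the note from a willing subject. It leaves in place the data to which the refusal related. The likeliest alternative meaning moves the deletion to on-study adverse events that must be documented and retained.

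The main loss is in the study's own safety record, the 10.4.4 summaries and the 10-subject FDA summary. A downward bias in adverse event incidence is plausible, because people may leave on account of device or surgical problems, but the documents do not show that such subjects are the ones who refuse. No magnitude is claimed. The textual conflict depends on no rate; it assumes only that safety records count as data in the record system, which is the natural reading where no exception is stated.

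**What to change.** Rewrite the data paragraph of 5.4.2 to say two things:

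1. Which research data (efficacy and exploratory) are removed when a subject refuses, and whether they are those collected before the note, after it, or both.
2. That adverse event, serious adverse event, device and termination-visit safety records made up to withdrawal, and within the existing 8.3 and 8.4.2 windows, are kept. They are counted in the 10.4.4 summaries, the 10-subject FDA summary and the halting count in 8.5.

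Reconcile the new text with 7.3.6, 8.3, 8.4.2, 10.4.2 and 14.2. In 10.4.2, say whether a refusal under 5.4.2 is a request for removal, and state the last day of participation for a subject who withdraws. Align the consent wording, which is not in the public documents and so cannot be checked here.

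The cost is one paragraph, a few cross-references and matching consent text. No visit or contact is added. The downside is small: a withdrawing subject has less control over safety records.

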5.5 PREMATURE TERMINATION OR SUSPENSION OF STUDY

This study may be temporarily suspended or prematurely terminated if there is sufficient reasonable cause. If the study is prematurely terminated or suspended, the PI will promptly inform the IRB and will provide the reason(s) for the termination or suspension. Circumstances that may warrant termination or suspension include, but are not limited to:

- Determination of unexpected, significant, or unacceptable risk to participants
- Demonstration of efficacy that would warrant stopping
- Insufficient compliance to protocol requirements
- Data that are not sufficiently complete and/or evaluable
- Determination of futility

Study may resume once concerns about safety, protocol compliance, data quality are addressed and satisfy the sponsor, IRB and/or FDA.

6 STUDY INTERVENTION/INVESTIGATIONAL PRODUCT

6.1 STUDY PRODUCT DESCRIPTION

6.1.1 ACQUISITION

The spinal cord stimulator system (epidural stimulator, extension lead, and Tripole paddle) will be obtained directly from St. Jude Medical. The devices and accessories will be shipped from their production facilities to Hennepin County Medical Center and the Minneapolis VA Health Care System and will be disbursed to the principal investigator according to a Material Transfer Agreement to be arranged between Hennepin County Medical Center, the Minneapolis VA Health Care System, and St. Jude Medical.

6.1.2 FORMULATION, APPEARANCE, PACKAGING, AND LABELING

The products are the St. Jude Medical Proclaim™ Elite Implantable Pulse Generator and Tripole™ 16 Lead paddle leads. The Implantable Pulse Generator and lead accessories will be enclosed in separately packaged kits including accessories necessary for surgical implantation. The kits will use the commercial box appearance, which includes the name of the product, the model number, a description of the product, safety, use, and storage information, and manufacturer contact information. A label will be affixed on each product box with large text stating that the products are for a clinical study and the name of this clinical study. In addition to the device kits, the standard product manual package insert will be included, which details prescription and safety information, a description of the product, directions for use, technical support, product specifications, regulatory statements, a component list, and packaging symbol and definition legends. On this insert, an affixed label will instruct users to consult an additional study specific package insert that will also be included for use modifications. This package insert will contain the name and description of this clinical study, new directions for use detailing the study indications and study procedure, and contact information for the study investigators.

This product is commercially marketed and FDA approved for use in chronic, intractable pain of the trunk and/or limbs, including unilateral or bilateral pain associated with failed back surgery syndrome and intractable low back and leg pain. The products will be used without pre-implantation modification, but the method of implantation will be modified as described in 6.1.4.

6.1.3 PRODUCT STORAGE AND STABILITY

No seal will be broken until the operating surgeon is ready to implant the devices in the surgical field. Expiration dates will be verified before any seal is broken. Products will be housed in a locked cabinet according to the instruction manual specifications for temperature, humidity, and pressure. The cabinet will be accessible to only the principal and co investigators until use if delivered before the planned surgery.

Products will be housed in the Hennepin Central Core storage facility managed by [name]. Products will be housed in the Minneapolis VA Central Core, 2M-2Q, managed by [name], the head of OR. Products will be housed in the University of Minnesota Medical Center Central Supply, managed by [name].

6.1.4 ADMINISTRATION OF STUDY INTERVENTION/INVESTIGATIONAL PRODUCT

Surgical implantation of the product will be similar to implantation for patients with chronic pain, which is a routine neurosurgical operation. A single level laminectomy will be performed to allow placement of the paddle electrode under fluoroscopic guidance at the T11-T12 area to cover spinal cord segments L1-S1. Intraoperative neuromonitoring with EMG will be performed to verify the coverage and placement of the epidural stimulator paddles with suprathreshold stimulation. A subcutaneous pocket will be created where the neurostimulator will be placed. The paddle electrode wire will be tunneled in the subcutaneous space to the pocket and connected to the neurostimulator. Surgery will be performed in the standard fashion, under sterile conditions.

6.1.5 MODIFICATION OF STUDY INTERVENTION/INVESTIGATIONAL PRODUCT FOR A PARTICIPANT

The device will not be modified for any subject at any time.

6.1.11 DEVICE SPECIFIC CONSIDERATIONS

The St. Jude Medical Proclaim™ Elite 7 Implantable Pulse Generator (Model 3662ANS) is 66.8mm x 50.2mm x 13.5mm. The St. Jude Medical Tripole™ Paddle Leads (Model 3219) are 57.0mm x 10.0mm x 1.6mm with a 60cm lead wire. The pulse width, frequency, and amplitude programming settings of the implantable pulse generator will be within the established parameters in the commercial product manual, and the settings for each study member will vary according to the experimental protocol (as optimization of stimulator settings is one of the main study aims). The duration of implantation will be for 6.5 years (the longevity of the device battery) or until device malfunction or complications / medical issues requiring explantation of the device. Exposure to stimulation is detailed in the study procedures, but is summarized as an average of 2 hours of intermittent stimulation per monthly session and up to four hours per day, 5 days a week for home training sessions over the course of 15 months.

6.2 STUDY AGENT ACCOUNTABILITY PROCEDURES

Devices will be distributed to the Hennepin County Medical Center, University of Minnesota, and the Minneapolis VA Health Care System according to a Materials Transfer Agreement between these sites, which will specify device ownership, storage, and use. The products will be shipped two at a time prior to the surgical implantation procedure for each pair of subjects after recruitment once the subjects have been fully screened.

The products will be received by hospital personnel trained in the safe handling of this equipment and informed of proper interim storage requirements, and the senior study investigators will receive these devices from interim

storage to place in the locked appropriate operating room storage area. Documentation of the proper receipt and transfer of all study products will be maintained by the hospitals and study personnel according to the standards of the Materials Transfer Agreement and hospital policy. Should study products be unused and not defective or expired, they will be assigned to the next applicable study subject should the product not expire before the anticipated next surgery date. Otherwise, the product will be disposed of or returned to St. Jude Medical. Defective, damaged, or expired products will be reported to St. Jude Medical and disposed of or otherwise processed according to hospital and manufacturer policy.

7 STUDY PROCEDURES AND SCHEDULE

7.1 STUDY PROCEDURES/EVALUATIONS

7.1.1 STUDY SPECIFIC PROCEDURES

The following is a list of procedures to be performed at various time points throughout the study according to the schedule in Table 1. Please see that table for information about timing. Most assessments are in concordance with the NIH NINDS SCI CDE recommendations in addition to the NIH NIBIB Working group on epidural stimulation trials.

Table 1

Categories	Data Element Name
Demographics	General Core
	Demographics
General Health History	Medical History
	Prior and Concomitant Medications
	Family History
Epidemiology/Environmental History	Alcohol and Tobacco Use
	Alcohol Use Disorders Identification Test (AUDIT)
	Substance Use
History of Disease/Injury Event	History of Injury
	Rehabilitation Therapies
Physical Examinations	Clinical Assessment
	Physical Exam
	Braden Scale for Predicting Pressure Sore Risk
Vital Signs and Other Body Measures	Vital Signs Tests
	Laboratory Tests
Spinal Imaging / Spinal Cord Imaging	Imaging SCI
	Magnetic Resonance Imaging
Treatment / Intervention Data	Assistive/Mobility Devices & Orthosis
	Rehabilitation Therapies
	Surgical and Procedural Interventions
	Other Investigational Treatments
	Home Training Remote Accelerometer Assessment
Neurological Outcomes	International Standards for Neurological Classification of SCI Worksheet

	Modified Ashworth Scale
	NINDS Myotatic Reflex Scale
Electrodiagnostics	Brain Motor Control Assessment
	Device electrode mapping
	Standing Training Assessment
Functional Outcomes	Capabilities of Upper Extremity Questionnaire
	Spinal Cord Independence Measure
	Wheelchair Skills Test
	Falls Diary
	Neurogenic Bladder Symptom Score
	Neurogenic Bowel Dysfunction Score
Autonomic Assessments	Sympathetic skin responses (SSR)
	Tilt Table Testing
	Home Blood Pressure Monitoring
	Orthostatics
	Cardiac Structure and Function Assessments
	Cerebrovascular Assessment
	Arterial Stiffness
	Arterial structure: Wall thickness and lumen diameter
Cognitive	Visual Neurocognitive Assessment
Pain	International SCI Pain Basic Data Subset
Psychological	Patient Health Questionnaire - 9 (PHQ-9) Depression Scale
Quality of Life	Spinal Cord Injury - Quality of Life (SCI-QOL)
	World Health Organization Quality of Life Assessment (WHOQOL-BREF)
Sleep	Epworth Sleepiness Scale (ESS)

STANDARD PROCEDURES

Standardized CRFs will be administered in content groups according to the above organization. What follows is a description of the procedures of each content group. Content groups with simple administration guidelines will be administered according to the practices outlined in current CDEs that will be used and will not be further explained here.

Participant History and Family History

Medical History will be obtained preliminarily from patient medical records, with incomplete entries to be filled during the second subject encounter. The timeframe for eligible history elements will be complete as possible with no limit on the age of diagnosis onset. Medication history will include current medications only, with the exception of botulinum toxin according to the exclusion criteria. A questionnaire about alcohol use including the AUDIT will be administered via interview. The subject will be appropriately informed of the results of the alcohol and drug screening tests and referred to counseling if indicated.

Disease/Injury Related Events

A history of injury will be obtained from the subject's medical records and from the subject, with medical records taking priority when descriptions of the event diverge. Rehabilitation therapy history will apply to all events occurring after the initial injury.

Assessments and Examinations

A full physical examination will be performed. An SCI-focused clinical assessment will be completed from the patient medical records, subject interviews, interviews of trusted collateral individuals with subject verbal consent, and from the full physical examination. The Braden Scale will be used in a clinical determination of the subject's ability to participate in all elements of the study.

Complete vital signs will be obtained during enrollment. These measures include: height, weight, pulse, blood pressure, and temperature. Height, weight, pulse, blood pressure, and temperature will be taken at the beginning and the end of every 3rd month visit (3, 6, 9, 12, 15) to screen for autonomic dysreflexia. Laboratory tests will include only a lipid profile.

The scan date, time, and type of imaging study of one high quality spinal imaging study at the time of spinal cord injury and all subsequent spinal imaging studies will be obtained according to the Imaging SCI Case Report Form. This information and the content of the imaging study as analyzed by appropriately trained members of the investigation team and/or the impression by the reading radiologist will be obtained for one high quality spinal MRI at the time of spinal cord injury and the most recent study after the event. If there is no high quality MRI after the time of spinal cord injury, the subject will be scheduled for a spinal MRI study during enrollment.

All procedures listed in this section will be explained in detail in the MOP, and will be performed according to standard clinical procedure in the institution. The subject will be informed of the results of these clinical tests, and their primary care provider will be informed. The results of these tests will be entered into the subject's chart.

SCI Classification

The international standards for neurological classification of SCI will be obtained in full during a complete physical exam. A spasticity assessment will be obtained during physical exam for all major limb movements. After the surgical intervention, spasticity assessments will be used at the beginning and end of every 3rd month visit (3, 6, 9, 12, 15) to screen for uncontrolled spasticity in the lower limbs. Peripheral reflexes will also be measured during every 3rd monthly visit.

Functional Outcome

The Capabilities of Upper Extremity Questionnaire and Spinal Cord Independence Measure will be administered during a screening/enrollment clinical visit using subject responses. The Wheelchair Skills test will be administered by a clinician investigator during a screening/enrollment clinical visit.

Autonomic Assessments are all study specific and will be explained in the modified procedures section.

The International SCI Pain Basic Data Subset will be administered during a subject interview.

The Patient Health Questionnaire Depression Scale and Hospital Anxiety and Depression Scale will be administered during a subject visit. Positive psychiatric screening will result in a referral to the appropriate services. Positive suicidal / homicidal ideation or intention to harm self or others will result in a referral to the appropriate services and immediate prompting of the proper authorities.

The Epworth Sleepiness Scale will be administered during a subject interview.

Falls Diary

The falls diary will be a subject-maintained log of fall events. The information will include the time and date of the fall, the activity prior to the fall, the estimated height of the fall, the presence of head or bodily injury after the fall, and subject recorded medical information such as the need for hospitalization and diagnoses related to the falls.

Urinary Function

Urinary function will be assessed through the Neurogenic Bladder Symptom Score (NBSS) survey.

Bowel Function

Bowel function will be assessed through the Neurogenic Bowel Dysfunction Score survey.

MODIFIED PROCEDURES

Modified procedures are listed in detail below. All procedures are explained in working detail in the MOP.

Treatment/Intervention Data

Home Training

Home training allows use of the epidural stimulator while completing a computer-guided accelerometer-based task. Subjects will fasten two wireless accelerometers to their feet to detect plantarflexion and dorsiflexion as well as gross translational movement in the legs.

Our group has developed an android app that cues the subject to move the left or right foot in a randomized fashion. As the subject moves their legs, the accelerometry data will be collected wirelessly and stored. This data will include the subject number, date and time logs, stimulator setting number, and accelerometry data. The stored data will be automatically uploaded to a HIPAA-compliant and secure server. Post-processing will allow calculation of maximum velocity and fidelity of volition.

After the first visit, subjects will be given detailed instructions on their home stimulation program, which allows up to four hours per day of epidural stimulation. At each follow-up visit, the subjects' SCS programmers will be customized with 5 subject settings. Only experimental stimulator configurations (no sham settings) will be used. Subjects will receive a paper calendar with assigned subject settings for one hour of training 5 times per week. Subjects are expected to turn the stimulator on for training, but can otherwise use the stimulator up to 4 hours per day as needed. Subjects will be instructed to undergo a formal regimen of exercises and will be supplied with a tablet computer capable of cuing subjects with audio and video through the exercises and tracking wireless accelerometer data during the session. Fidelity of the volition cuing will be calculated as a percentage of the training session when the entire training session is completed. Maximum velocities will be aggregated over the training session and parameterized for comparison with repeated measures ANOVA. Stimulator use time will be logged and factored into data analysis.

Electrodiagnostics

Brain Motor Control Assessment. 60 minutes.

The subject's quadriceps, adductors, hamstrings, tibialis anterior, and triceps surae muscles of each leg, as well as the midline over the abdominal muscles at the level of the umbilicus and the lumbar paraspinal muscles will be recorded with multichannel surface EMG. Upper leg and ankle accelerometers will also be monitored to test for presence of movement. Subjects will undergo relaxation, voluntary and passive hip and knee flexion, and voluntary and passive ankle dorsiflexion and plantarflexion during trials of computer controlled patterns and levels of epidural stimulation (or sham). Stimulation and sham programs, defined as stimulator settings that either involve an experimental stimulation configuration or no stimulation through any lead, will be randomly assigned in a group of repeated trials during the session. The BMCA Lower-Limb Protocol elements of Relaxation, Voluntary movements, and Passive stretch will be used to gather quantitative EMG data. Accelerometer data will be quantified by presence and rate of acceleration.

Device electrode custom mapping assessment

To be performed on the first visit after the surgery (month 3). Epidural spinal cord stimulator mapping is similar in concept to a nerve conduction study, with the stimulus coming from one of the epidural stimulator leads as opposed to the same nerve. The purpose of mapping is to define which stimulator leads are associated with the voluntary function of the muscles of interest in the legs, so leads that do not appear to result in any motor activation are excluded from programming trials. The procedure will be performed in the same manner as the Brain Motor Control Assessment, but the computer will stimulate one electrode at a time for each series of volitional tests until all electrodes have been independently stimulated. Electrodes that do not generate a volitional EMG signal will not be included in the set of computer controlled stimulator patterns for the Brain Motor Control Assessment. Accelerometers will not be used.

Standing Training Assessment

The subject will be placed in a standing assist harness in a seated position. The subject's quadriceps, adductors, hamstrings, tibialis anterior, and triceps surae muscles of each leg, as well as the midline over the abdominal muscles at the level of the umbilicus and the lumbar paraspinal muscles will be recorded with multichannel surface EMG. The subject will be given a randomized experimental or sham stimulator setting. During recording, the subject will be assisted from sitting to standing, with parallel bars and research investigators as upper body support. The subject will then shift their weight between the left and right side of their body on cue while their feet are placed on a scale that measures weight distribution. The subject will be assisted back into a seated position. This will be repeated until the set of experimental and sham stimulator settings is complete. Data collected will be EMG signal activation while transitioning to stand, EMG activity while shifting weight, and the changes in weight on the left and right side of the scale during volitional weight shifting.

Autonomic Screening

Screening Tilt Table Testing

The subject will be asked to lay in the supine position on a tilt table. A blood pressure monitor will be applied to the patient. The subject's blood pressure will be taken and considered as the baseline. The subject will then be passively moved to a standing position, while having a blood pressure reading taken every minute for ten minutes. A Systolic Blood Pressure decrease of 20mmHg from baseline is considered positive. A physician investigator will observe the patient during the procedure and ask for symptoms of syncope or presyncope during and after the test. Any signs or symptoms of syncope or presyncope will be considered positive.

Home Blood Pressure Monitoring

The subject will be asked to wear a blood pressure monitor at home for twenty four hours. The subject's Systolic Blood Pressure that was recorded as a baseline for Tilt-Table Testing will be utilized as the baseline for this assessment as well. During the twenty four hour period, a Systolic Blood pressure increase of 20mmHg will be considered positive. A physician investigator will debrief the patient following this period and ask for symptoms of syncope or presyncope during and after the period. Any signs or symptoms of syncope or presyncope will be considered positive.

Autonomic Assessments

Tilt Table Testing

This assessment will be performed during screening. The subject will be asked to lay in the supine position on a tilt table. A blood pressure monitor will be applied to the patient. The subject will then be passively moved to a standing position. Systolic Blood Pressure levels below 50 or above 200 are considered positive. A physician investigator will observe the patient during the procedure and ask for symptoms of syncope or presyncope during and after the test. Any signs or symptoms of syncope or presyncope will be considered positive.

Sympathetic skin responses (SSR)

We will utilize a well-established protocol to record SSR. The SSR will be elicited by stimulation of median and tibial nerves, and recorded bilaterally and simultaneously from both hands and feet to assess the extent of disruption to spinal autonomic pathways. Ten electrical stimuli (duration 0.2ms; intensity 8-10mA) will be applied to the left median nerve and left posterior tibial nerve, in random order and with variable and long-time delays to minimize habituation.

Orthostatic Sit-Up Test. 25 minutes.

